#### **6.4 Concomitant Medications and Treatments**

Concomitant medications will be recorded for any AE with onset  $\leq 28$  days post-vaccination and for any SAEs that occurs throughout the study. Details on concomitant medications to be recorded include the generic and/or trade name, over-the-counter or herbal, indication, dosage, regimen, route of administration, and start and end dates of the medication.

The following concomitant medications are prohibited during the study; however, they must not be withheld by the treating physician if clinically indicated:

- Any investigational drug/vaccine other than the study vaccines
- Pneumococcal vaccine other than the blinded study vaccine
- Planned vaccines (e.g., influenza, etc.)
- Chronic administration (defined as more than 14 days) of immunosuppressant or other immune modifying agents. For corticosteroids, this means prednisone or equivalent  $>10$  mg per day; topical and inhaled steroids are allowed.
- Administration of immunoglobulins or any blood products during the study period

Use of any prohibited medication must be recorded in the CRF. Whether a participant who uses a prohibited medication will be included in the per protocol (PP) population will be evaluated on a case-by-case basis.

#### **6.5 Emergency Unblinding Procedure**

In the event of a medical emergency, the PI and/or site investigator may require that the blind be broken for the participant experiencing the emergency when knowledge of the participant's treatment assignment may influence the participant's clinical care. Every effort will be made not to unblind the participant unless it is considered absolutely necessary for the welfare of the participant. Prior to unblinding, the investigator is encouraged (to the extent possible, without jeopardizing the participant's health) to contact the Sponsor (or designee) to discuss the decision to break the blind.

The PI and/or site investigator will be expected to provide a rationale for the necessity of unblinding, based on the expectation that knowledge of the participant's treatment assignment will have a meaningful impact on the participant's medical care in the short term. If a participant's treatment assignment is unblinded, the participant will remain in the study and continue with protocol-defined

study visits and procedures, unless there is another reason for participant discontinuation. The decision to unblind will be communicated to all regulatory bodies as required. At the end of the study, documentation of all unblinded participants (and the rationale for unblinding) will be incorporated into the trial master file.

## **6.6 Management of Pregnancy**

All WOCBP will be monitored for the use of adequate contraception until completion of Visit 3. At Visit 3, WOCBP will have a pregnancy test and will be monitored for pregnancy until end of study Visit 4.

Any WOCBP who become pregnant during the study will be followed to term, and the following information will be gathered in regard to the pregnancy outcome: date of delivery and health status of the mother and child, including the child's gender, height, and weight. Complications and/or abnormalities must be reported, including any premature terminations. A pregnancy is reported as an AE or SAE only when there is suspicion that the investigational product may have interfered with the effectiveness of contraception or there was a serious complication in the pregnancy, including a spontaneous abortion or an elective termination for medical reasons. Pregnancies that occur up to Visit 3 (Day 29) will be included in the interim analysis (primary analysis) and the CSR, and any pregnancies that occur after Day 29 through Visit 4 and the outcome of pregnancies will be reported to the Sponsor as part of the safety management plan.

The PI is required to notify the Sponsor (or designee) within 24 hours of knowledge of a pregnancy.

## **6.7 Clinical Procedures**

### **6.7.1 Vital Signs**

- Body temperature will be measured in degrees Celsius (recorded to the nearest 0.1 degree) by oral (sublingual) thermometer following at least 20 minutes of avoidance of food and drink.
- Respiratory rate will be measured in breaths per minute.
- Heart rate will be measured in beats per minute by automated device or manually, and not on the arm used for study vaccination in adults if an arm cuff is used.
- Blood pressure will be measured in millimeters (mm) of mercury by automated device or manually.
- Vital signs will be graded according to the toxicity grading scale in Appendix 3.

### **6.7.2 Height and Weight**

- Height will be measured in centimeters (cm) and recorded to the nearest 1 cm.
- Weight will be measured in kilograms (kg) and recorded to the nearest 0.1 kg.

### **6.7.3 Complete Physical Examination**

- A complete physical examination will include head, eyes, ears, nose, oropharynx, neck, chest

(auscultation), lymph nodes (neck, supraclavicular, axillary), back, abdomen (auscultation and palpation), musculoskeletal, skin (especially hands, arms, injection sites), and nervous system.

#### 6.7.4 Injection Site Examination

- Redness will be examined under standard lighting conditions and measured based on the maximum diameter and recorded to the nearest 1 mm.
- Swelling will be examined by palpation and visual inspection under standard lighting conditions; the examiner may temporarily mark the skin at the margins of visible swelling, then measure at the maximum diameter and record the distance to the nearest 1 mm.
- Local reactions will be graded according to the toxicity grading scale in Appendix 2.

### 7. LABORATORY EVALUATIONS

Blood samples will be collected from all participants for immunogenicity testing and for safety testing.

#### 7.1 Sample Collection, Distribution, and Storage

Samples to evaluate vaccine safety in adults will be obtained and processed at each trial site and transported to each site's clinical laboratory for testing. Research specimens collected for the immunogenicity endpoints will be separated into aliquots by each site's processing laboratory as per the Lab Manual and stored at  $\leq -70^{\circ}\text{C}$  in their storage facilities before being shipped to the central immunology laboratories (see Section 7.3). Continuous temperature monitoring and backup generators will be in place to ensure proper sample storage.

Volumes of blood required for adults are shown in Table 10. These volumes are for the expected standard laboratory testing; retesting may require additional blood draws. Provision for additional blood draws (for the purposes of safety assessments) will be included in the ICF.

**Table 10. Total Blood Volume Required (Adults)**

Category Tests	Visit 0	Visit 1	Visit 2	Visit 3	Total
Hematology WBC, Hgb, Plts	4 mL	-	4 mL	-	8 mL
Chemistry ALT, AST, creatinine	3 mL	-	3 mL	-	6 mL
Pregnancy TestA hCG (serum or urine pregnancy test)	5 mL	-	-	-	5 mLC
Viral Serology HIV1/2 Ab, HBsAg, HCV Ab	5 mL	-	-	-	5 mL

Category Tests	Visit 0	Visit 1	Visit 2	Visit 3	Total
Immunogenicity Assays Serotype-specific B IgG and OPA	-	50 mL	-	50 mL	100 mL
Total Blood Volume	17 mL	50 mL	7 mL	50 mL	124 mLC

A In WOCBP only. Urine pregnancy test acceptable

B 1, 2, 3, 4, 5, 6A, 6B, 6C, 7F, 8, 9N, 9V, 10A, 12F, 14, 15A, 15B, 16F, 18C, 19A, 19F, 22F, 23F, 24F, 33F, 35B

C Maximum blood volume (assumes participant is a WOCBP)

Urine samples will be collected from WOCBP on Day 1 and Day 29 for pregnancy testing.

## 7.2 Clinical Laboratory Assays

Protocol-mandated screening and clinical safety laboratory tests in participants will be performed at site clinical labs, which provides Clinical Laboratory Improvement Amendments -certified comprehensive clinical laboratory services.

If clinically significant abnormalities are identified during screening, participants will be referred for further medical management. If identified during the study, participants may be asked to return to the study site for further evaluation, including clinical evaluation and repeat laboratory testing as warranted.

## 7.3 Immunological Assays

The following immunological assays are to be undertaken:

- IgG concentration: The serum IgG concentration to each of the 25 serotypes contained in IVT PCV-25- (1, 2, 3, 4, 5, 6B, 6C, 7F, 8, 9N, 9V, 10A, 12F, 14, 15A, 15B, 16F, 18C, 19A, 19F, 22F, 23F, 24F, 33F, 35B) as well as serotype 6A, will be measured in a validated assay (E.g. ELISA, electrochemiluminescence immunoassay, meso scale discovery, etc.) in serum samples collected at Visits 1 and 3.

- OPA: The functional activity of the serum antibody to each of the 25 serotypes contained in IVT PCV-25 (1, 2, 3, 4, 5, 6B, 6C, 7F, 8, 9N, 9V, 10A, 12F, 14, 15A, 15B, 16F, 18C, 19A, 19F, 22F, 23F, 24F, 33F, 35B) as well as serotype 6A, will be determined in serum samples collected at Visits 1 and 3. This activity will be determined using the 4-fold multiplexed OPA (MOPA) developed at the

Alternative testing sites may be considered if the serotype-specific OPA assay has been validated.

## 7.4 Assay Qualification, Standardization, and Validation

Assays employed to evaluate the primary safety laboratory endpoint in adults have been properly validated and will be run with adequate controls. The IgG and MOPA that will be used to measure

the magnitude and the functional activity of the pneumococcal polysaccharide antibody responses constituting secondary endpoints of the trial are standardly used in the field to measure immunogenicity as a surrogate marker for efficacy of PCVs. The IgG has been

Both

assays will be run with adequate controls.

## **7.5 Biohazard Containment**

As transmission of blood-borne pathogens can occur through contact with contaminated needles, blood, and blood products, appropriate blood and secretion precautions will be employed by all personnel in the drawing of blood and handling and shipping of all specimens for this study, as recommended by the US Centers for Disease Control and Prevention. All dangerous goods materials, including diagnostic specimens and infectious substances, must be transported according to instructions detailed in the International Air Transport Association (IATA) Dangerous Goods Regulations. Biohazardous waste will be contained according to institutional, transportation/carrier, and all other applicable regulations.

## **8. SAFETY ASSESSMENT AND REPORTING**

The PI is responsible for the detection and documentation of events meeting the criteria and definition of an AE or SAE as provided in this protocol for the duration of the study.

### **8.1 Collection of Safety Events**

AEs will be systematically collected at all study visits. Solicited AEs will be assessed in all participants immediately (30 minutes) after each vaccination. Subjects will record solicited AEs daily in the memory aid for the 7 days (Day 1 and the following 6 days) following vaccination, as well as record unsolicited AEs that occur prior to the 7- or 28-day follow-up visit (If a solicited AE is ongoing at 7 days post-vaccination, or occurs after 7 days post-vaccination, the event will be followed as per AE monitoring requirements. Clinically significant laboratory abnormalities in adult participants will also be recorded as an unsolicited AE.

SAEs will be recorded throughout the entire study period.

Medical events which occur between the time of enrollment (signed informed consent) and randomization for all participants regardless of screening outcome will be captured on the medical history form.

## **8.2 Definitions**

### **8.2.1 Adverse Event**

An AE, as defined in this protocol, is any untoward medical occurrence in a participant administered an investigational vaccine and which does not necessarily have a causal relationship with this treatment. An AE can therefore be any unfavorable and unintended sign (including an abnormal laboratory finding), symptom, or disease temporally associated with the use of an investigational product. An AE will be documented as to whether or not it is considered to be related to study vaccine. An AE includes, but is not limited to, the following:

- An intercurrent illness or injury during the course of the study after receipt of an investigational product
- Any clinically significant worsening of a preexisting condition after receipt of an investigational product

A medical condition, in the form of signs, symptoms, disease, or laboratory or psychological/physiologic observations, occurring in a participant from whom consent has been obtained but prior to having received a study vaccine is not classified as an AE but will be captured and recorded on the medical history form.

### **8.2.2 Solicited AE**

Solicited AEs are pre-specified local (injection-site specific) and systemic AEs that occur relatively more frequently, or are known to be associated with vaccination, and which are monitored actively as potential indicators of vaccine reactogenicity. Investigators will not be required to assess causality of solicited AEs if the onset is during the solicitation period.

The following specific solicited AEs will be monitored:

Local solicited AEs:

- Pain and/or tenderness
- Swelling
- Redness

Systemic solicited AEs:

- Fever (defined as body temperature  $\geq 38^{\circ}\text{C}$ )
- Headache
- Fatigue
- Myalgia
- Arthralgia
- Rash

### 8.2.3 Unsolicited AE

An unsolicited adverse event is any AE reported spontaneously by the participant, observed by the study staff during study visits, or those identified during review of medical records or source documents. Solicited AEs with an onset after the 7-day solicitation period will be considered unsolicited AEs. In the absence of a diagnosis, abnormal physical examination findings, or abnormal clinical safety laboratory test results that are assessed by the investigator to be clinically significant will be recorded as an AE.

### 8.2.4 Serious Adverse Event

An SAE is a specific AE that:

- Results in death.
- Is life-threatening.\*
- Requires inpatient hospitalization or prolongation of an existing hospitalization.\*\*
- Results in a persistent or significant disability or incapacity.\*\*\*
- Results in a congenital anomaly or birth defect.

**\*Life-threatening** refers to immediate risk of death as the event occurred per the reporter. A life-threatening event does not include an event that, had it occurred in a more severe form, might have caused death but, as it actually occurred, did not create an immediate risk of death.

For example, hepatitis that resolved without evidence of hepatic failure would not be considered life-threatening, even though hepatitis of a more severe nature can be fatal. Similarly, an allergic reaction resulting in angioedema of the face would not be life-threatening, even though angioedema of the larynx, allergic bronchospasm, or anaphylaxis can be fatal.

**\*\*Hospitalization** is an admission to a health facility in the situation where there is an AE. A period of observation at a clinical trial site is not considered to represent hospitalization for the purposes of SAE reporting. Hospitalization or prolongation of a hospitalization constitutes a criterion for an AE to be serious; however, it is not in itself considered a SAE. In absence of an AE, a hospitalization or prolongation of a hospitalization should not be reported as an SAE by the PI on a SAE form. Such situations include, but are not limited to, the following:

- A hospitalization for a preexisting condition that has not worsened.
- Hospitalization for social reasons.

**\*\*\*Disability** is defined as a substantial disruption in a person's ability to conduct normal life functions. If there is any doubt about whether the information constitutes an SAE, the information is treated as an SAE.

Medical and scientific judgment should be exercised in deciding whether expedited reporting is appropriate in other situations, such as important medical events that may not be immediately life-

threatening or result in death or hospitalization but may jeopardize the patient or may require intervention to prevent one of the other outcomes listed in the definition above. These should also usually be considered serious. Examples of such events are intensive treatment in an emergency room or at home for allergic bronchospasm, or blood dyscrasias or convulsions that do not result in hospitalization.

### 8.2.5 Severity (Intensity) of an AE

The severity of all solicited AEs will be graded from Mild (Grade 1) to Potentially Life Threatening (Grade 4), based on the criteria given in Appendix 2. All AEs leading to death are Grade 5 events. AEs are graded based on the worst severity grade during the illness/symptoms. All other unsolicited AEs will be classified as an AE and graded based on the AE severity scale in Table 11 below. The grading scales for solicited and unsolicited AEs used in this study have been derived from the *Division of AIDS (DAIDS) Table for Grading the Severity of Adult and Pediatric Adverse Events* (Version 2.1, July 2017), from the US National Institutes of Health, and from *Guidance for Industry, Toxicity Grading Scale for Healthy Adult and Adolescent Volunteers Enrolled in Preventive Vaccine Clinical Trials*, U.S. Department of Health and Human Services, FDA, CBER, September 2007.

**Table 11. Severity Grading for Unsolicited AEs**

Grade	Description
1	Causes no or minimal interference with normal daily activities; intervention not indicated
2	Interferes with but does not prevent normal daily activities; no or minimal medical intervention/therapy required
3	Prevents normal daily activities; intervention or hospitalization indicated
4	Causes inability to perform basic self-care activities (adults only); intervention indicated to prevent permanent impairment, persistent disability, or death

### 8.2.6 Causal Relationship of an AE

A suspected adverse drug reaction (ADR) means any AE for which there is a reasonable possibility that the study vaccine caused the AE. A reasonable possibility means there is evidence to suggest a causal relationship between the vaccine and the AE. All cases judged by either the PI or the Sponsor (or designee) as having a reasonable suspected causal relationship to the study vaccine will qualify as ADRs. Medical judgment will be used to determine the relationship, considering all relevant factors, including pattern of reaction, temporal relationship, confounding factors such as concomitant medications, concomitant diseases, and relevant history.

The likelihood of the relationship of the AE to study vaccine is to be recorded as follows:

- Related: There is a reasonable causal relationship between the vaccine administered and the AE.
- Not Related: There is no reasonable causal relationship between the vaccine administered and the AE.

Note: solicited reactogenicity events will not be judged for relatedness.

### **8.2.7 Assessment of Outcome of AE**

The outcome of the AE will be assessed and recorded as per the following categories:

- Ongoing.
- Recovered/resolved.
- Recovered/resolved with sequelae.
- Fatal.
- Unknown.

## **8.3 AE Recording and Reporting**

All AEs will be recorded and reported after receipt of each study vaccine through 28 days post-vaccination (Visit 3). SAEs will be recorded throughout the entire study period.

The study staff must completely and promptly record each AE in the source documentation and on the relevant CRF, regardless of relationship to the vaccine administered or procedure as determined by the PI. The PI will attempt, if possible, to establish a diagnosis based on the signs and symptoms. When a diagnosis for the reported signs or symptoms is known, the PI will report the diagnosis as the AE, not the signs and symptoms. AEs will be classified by the Medical Dictionary for Regulatory Activities (MedDRA) term and by severity, relatedness, and outcome.

Reporting of AEs will follow the regulatory guidelines of Health Canada, the local ethics committees (ECs), WCG IRB, and the PATH Office of Research Affairs (ORA) in regard to requirements, processes, and forms.

## **8.4 SAE Reporting**

If an AE is classified as serious, an SAE form will be completed and submitted within 24 hours of the PI becoming aware of the SAE, including information on the location, severity, relatedness, and clinical summary of the event to the Sponsor (or designee) to initiate any DSMB evaluation, and any additional reporting requirements. The SAE submission will follow the regulatory guidelines of Health Canada, the local ECs, WCG IRB, and PATH ORA in regard to requirements, processes and forms. SAEs deemed related to study vaccine that are ongoing at the time of last participant last visit (LSLV) will continue to be followed until resolved, assessed to be resolved with sequelae, or assessed to be stable/chronic. SAEs deemed not related to study vaccine that are unresolved at the time of LSLV will be classified as ongoing.

### **8.4.1 Unanticipated Problems**

Unanticipated problems will be submitted to Health Canada, the local ECs, WCG IRB, and PATH ORA per reporting requirements of each regulatory body. All serious unanticipated problems involving risk to participants or others will be promptly (within 48 hours) reported by telephone, by email, or by facsimile to the Sponsor (or designee). Follow-up reports will be submitted as soon as additional information becomes available.

## **9. SAFETY MONITORING**

The PI will be responsible for continuous monitoring of all study participants' safety. In case of urgent need, participants will have the means to get in contact with study staff at any time (24 hours per day). The PI will also be available by cell phone 24-hours per day for medical emergencies. Weekly notifications of group-blinded Grade 3 or greater AEs will be sent to the PI, site investigators, CRO Medical Monitor, PATH Medical Officer (MO), and Inventprise's Chief Medical Officer (CMO) for situational awareness and ongoing safety assessment.

### **9.1 Data Safety Monitoring Board**

A DSMB, composed of at least three independent members with expertise in vaccine clinical trials, will be convened to provide safety oversight. The DSMB will review unblinded safety and tolerability data after the last participant completes the 28-day follow-up visit (V3).

The DSMB will also meet on an ad hoc basis if a study pause rule is met (Section 9.2.) or upon the recommendation from the PI, PATH MO and Inventprise Inc.. In the event of a study pause, events will be unblinded, and no further enrollment will occur, and no study product will be administered until the DSMB approves lifting the pause.

DSMB reviews will indicate whether or not safety concerns were identified, and whether the trial should continue without change, be modified, or be terminated. The Sponsor will carefully consider the DSMB recommendations. If the Sponsor does not agree with these recommendations, a meeting will be held between the Sponsor CMO (or designee), PATH, PI, and DSMB to reach consensus on the appropriate action(s) to take in regard to the trial. However, if attempts to reach consensus fail, the Sponsor's opinion will prevail. In such situations, the Sponsor will inform Health Canada and local ECs of the Sponsor's perspective, and any changes to the trial.

The PI, PATH MO may also seek additional guidance from the DSMB as dictated by the occurrence of certain events that do not warrant a study pause.

The composition, responsibilities, and procedures of the DSMB will be detailed in the DSMB Charter.

## 9.2 Pause Rules

The DSMB will be convened if it is established that any of the following study pause rules has been met during the conduct of the trial:

- **Rule 1:** 1 or more participant experiences any vaccine-related Grade 4 AE or any vaccine-related SAE.
- **Rule 2:** 1 or more participant experiences Grade 3 or greater local reaction classified as related to vaccination by the PI: ulceration, necrosis, or sterile abscess at the injection site requiring drainage or surgical intervention.

**Rule 3:**  $\geq 5$  participants in the same group inclusive of participants from Groups A, B, C, and D that experience the same Grade 3 (or greater) AE or laboratory abnormality attributed (related) to study vaccine. In the case of fever and pain at the injection site, the episode must last longer than 48 hours, and, in the case of fever, be confirmed by the PI without evidence of other medical causes.

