#### **11.5.5 Analysis of Primary Objective**

All safety analyses will be conducted in the safety analysis population, according to the treatment received. Frequencies and percentages of participants with any solicited AE, solicited local AE, solicited systemic AE, unsolicited AE, clinical safety laboratory abnormality, SAE will be tabulated along with an exact two-sided 95% CI computed via the Clopper-Pearson method. The denominators for percentages will be the number of participants with the data available for analysis for the given endpoint. Participant-level data listing will be provided.

**Solicited local and systemic AEs:** All solicited AEs reported during 7 days post vaccination will be summarized according to defined severity grading scales. Frequencies and percentages of participants experiencing each solicited AE will be presented by treatment group and severity.

**Hematological and biochemical measurements:** For clinical safety laboratory data collected at screening and 7 days post-vaccination, individual Hgb, WBC count, Plts, AST, ALT, and creatinine values will be presented as number and percentage of participants out of range (above and below normal range as appropriate) and tabulated by toxicity grading and study group. In addition, summaries of changes from baseline will be presented. Clinically significant laboratory abnormalities will be considered an AE and relatedness will be reported.

**Unsolicited AEs:** All unsolicited AEs with onset occurring during the first 28 days post vaccination will be assessed for severity and relatedness to study product by the PI. Frequencies and percentages of participants with unsolicited AEs will be summarized by the SOC, PT, and treatment group. Similar summaries will be provided for severity and relatedness of the unsolicited AEs.

**SAEs:** All SAEs through Visit 4 (Day 169) will be recorded and summarized. Frequencies and percentages of participants with SAEs and relatedness to study vaccine of the events will be summarized by SOC, PT, and treatment group.

When an AE occurs more than once for a participant, the participant will be only counted once for the corresponding PT according to the maximum severity of the events. A summary table will be prepared for unsolicited AEs comprised of the following categories:

- Unsolicited AEs
- Related unsolicited AEs
- SAEs
- Related SAEs
- SAEs leading to death
- Unsolicited AEs leading to participant discontinuation

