## 16.2 Appendix 2: Solicited Local and Systemic Reactions Toxicity Grading Tables: Adults

Reaction	Mild (Grade 1)	Moderate (Grade 2)	Severe (Grade 3)	Potentially Life Threatening (Grade 4)
Pain at injection site (tenderness)	Does not interfere with activity / Mild discomfort to touch	Repeated use of non-narcotic pain reliever > 24 hours or interferes with activity/Discomfort with movement	Any use of narcotic pain reliever or prevents daily activity / Significant discomfort at rest	Emergency room (ER) visit or hospitalization
Redness at injection sitea	2.5 – 5 cm	5.1 – 10 cm	> 10 cm	N/A
Swelling at injection sitea	2.5 – 5 cm	5.1 – 10 cm	> 10 cm	N/A
Ulceration, Secondary infection, Sterile abscess, Drainage and/or Necrosis	N/A	N/A	Presence of any reaction and confirmed by site investigator	N/A
Fever (oral temp)	38.0 – 38.4°C	38.5 – 38.9°C	39.0 – 40°C	> 40°C
Headache	No interference with activity	Repeated use of non-narcotic pain reliever > 24 hours OR some interference with activity	Significant; any use Of narcotic pain reliever OR prevent daily activity	ER visit or hospitalization
Fatigue	No interference with activity	Some interference with activity	Significant; prevent daily activity	ER visit or hospitalization
Myalgia	No interference with activity	Some interference with activity	Significant; prevent daily activity	ER visit or hospitalization
Arthralgia	No interference with activity	Some interference with activity	Significant; prevent daily activity	ER visit or hospitalization

Reaction	Mild (Grade 1)	Moderate (Grade 2)	Severe (Grade 3)	Potentially Life Threatening (Grade 4)
Rash	Localized macular rash (not a local reaction at the site of injection)	Diffuse macular, maculopapular, or morbilliform rash OR target lesions	Diffuse macular, maculopapular, or morbilliform rash with vesicles or limited number of bullae OR superficial ulcerations of mucous membrane limited to one site	Extensive or generalized bulbous lesions OR Stevens-Johnson syndrome OR ulceration of mucous membrane involving two or more distinct mucosal sites OR toxic epidermal necrolysis (TEN)

a Redness and swelling should be measured at greatest surface diameter in millimeters using a ruler.

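### Pause Rule 3, and Rule 1 for non-serious Grade 4 events, count only vaccine-related events, yet solicited reactions are not judged for relatedness and no default attribution is stated

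*Protocol*

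**What the plan says.** **The rules.** Protocol 9.2 and SAP 5.2 give the same three pause rules. Rule 1 needs one vaccine-related Grade 4 AE or one vaccine-related SAE. Rule 3 needs at least five participants in a group with "the same Grade 3 (or greater) AE or laboratory abnormality attributed (related) to study vaccine". It then adds: "In the case of fever and pain at the injection site, the episode must last longer than 48 hours". Fever must also be confirmed by the PI with other medical causes excluded.

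**Causality of solicited events.** Fever, injection-site pain, headache, fatigue, myalgia, arthralgia, rash, redness and swelling are all solicited (Protocol 8.2.2). For these, 8.2.2 states: "Investigators will not be required to assess causality of solicited AEs if the onset is during the solicitation period". The note closing 8.2.6 goes further: "solicited reactogenicity events will not be judged for relatedness".

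**Text that points the other way.** Protocol 8.2.1 says in general terms that each AE is documented as related or not, and 8.3 has AEs classified by relatedness. Protocol 8.2.2 describes solicited events as relatively frequent "or are known to be associated with vaccination".

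**Analysis sections.** In Protocol 11.5.5 the PI is named as assessor for unsolicited AEs, which "will be assessed for severity and relatedness to study product by the PI". Relatedness is also reported for SAEs and for clinically significant laboratory abnormalities. Neither 11.5.5 nor SAP 4.6.5 mentions it for solicited events.

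**The concern.** A pause rule works only if the data it counts are collected. Rule 3 counts attributed events, and the protocol says that attribution will not be made for the class of event most likely to occur in the week after vaccination. Rule 3 is also the only pre-specified trigger for a cluster of severe but non-serious reactions.

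The timing makes this matter. The single scheduled DSMB review follows the last Day 29 visit (Protocol 9.1), when every dose has been given. The Protocol Summary expects about 10 months in total and up to 7 months per participant, which implies roughly 10 − 7 = 3 months of accrual before that point. The three formulations are new antigen and adjuvant combinations, and the safety data are meant to support moving directly to infants (Protocol 1.8). If five participants in one group report Grade 3 fatigue, site and sponsor staff would have to choose between two readings of the rule while dosing continues.

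**Working it through.** **Step 1. Which events have the input that the rule needs?**

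| Event | Relatedness collected? | Can it meet Rule 1 or 3 as written? |
|---|---|---|
| SAE, solicited or not | Yes (8.4) | Yes |
| Unsolicited AE | Yes, by the PI (11.5.5) | Yes |
| Clinically significant laboratory abnormality | Yes (11.5.5) | Yes |
| Non-serious Grade 3 solicited event in the 7-day window | 8.2.6 says no; 8.2.1 and 8.3 imply yes | Unclear (Rule 3) |
| Non-serious Grade 4 solicited event in the window | Same conflict | Unclear (Rule 1, and Rule 3) |

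Rule 2 is not affected. It asks for PI classification itself, and its reactions (ulceration, necrosis, sterile abscess) are not on the 8.2.2 list.

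**Step 2. How wide is the Rule 1 gap?** For pain, headache, fatigue, myalgia and arthralgia, Appendix 2 defines Grade 4 as "Emergency room (ER) visit or hospitalization". Hospitalization makes the event an SAE. Protocol 8.2.4 says intensive emergency-room treatment should usually be considered serious, and its disability note resolves doubt in favour of an SAE. What remains is mainly fever above 40°C and minor emergency-room visits.

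**Step 3. The plan's own figures.** The documents give no operating characteristics for the pause rules. The nearest stated figures are Protocol Table 12, the chance of at least one event, 1 − (1 − p)^n. For n = 60 and p = 5%: 1 − 0.95^60 = 0.954, as stated. All nine cells reproduce.

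**Step 4. How far apart are the two readings?** If solicited events are never attributed, their contribution to Rule 3 is 0. If they are deemed related, the chance that a group of size n reaches five is P(X ≥ 5) with X ~ Binomial(n, p), and the chance that some group does is 1 − ∏ P(X ≤ 4) over n = 40, 60, 80, 40.

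The rates are the Grade 3 counts in Protocol Table 6 (Phase 1, 60 adults, both arms combined, earlier formulation): fatigue 3, headache 2, myalgia 1. None of these carries the 48-hour condition.

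| Rate | n = 40 | n = 60 | n = 80 | Some group |
|---|---|---|---|---|
| 3/60 (5.0%) | 0.048 | 0.180 | 0.371 | 0.533 |
| 2/60 (3.3%) | 0.010 | 0.050 | 0.129 | 0.189 |
| 1/60 (1.7%) | 0.0005 | 0.003 | 0.011 | 0.015 |

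First row: 1 − 0.952 × 0.820 × 0.629 × 0.952 = 0.533.

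**Step 5. Uncertainty in the rates.** At the exact (Clopper-Pearson) 95% limits for each rate, the chance for some group runs from 0.2% to over 99.9% for fatigue (limits 1.0% and 13.9%), from about 0 to 99.8% for headache (0.4% and 11.5%), and from about 0 to 97.2% for myalgia (0.04% and 8.9%).

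**Step 6. The three event types together.** Table 6 shows 3 participants with any Grade 3 systemic event and 3 with Grade 3 fatigue. The headache and myalgia cases must therefore lie within those same 3 people. If that nesting holds here, five headaches in a group imply five fatigues, so the combined chance equals that for fatigue, about 53%.

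**The case against.** The strongest reply is that the intended reading is plain. Without solicited events, the sentence on fever and injection-site pain would have almost no effect. For fever, the rule builds in its own causal check through the PI. Protocol 8.2.2 says that assessment is not required, which does not forbid it, and 8.2.6 lets the sponsor as well as the PI judge causality. The DSMB Charter, which is not among the documents, may hold a default. Other safeguards run during dosing: participants are told to call about Grade 3 symptoms (6.2.2), weekly notices list Grade 3 or greater AEs (section 9), and the DSMB can meet ad hoc (9.1).

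Much of this stands. A reader might infer that solicited events are definitely excluded from the pause rules. The documents do not support that: they conflict, and the signs of intent favour counting them. A reader might also extend the gap to all Grade 4 solicited events; Step 2 shows that it is much narrower.

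The reply does not remove the conflict. The 8.2.6 note is unqualified, intent is not a stated default, and the other safeguards rest on judgement, which a pause rule is meant to replace. Automatic attribution cannot be assumed either. The Protocol Summary reports that Grade 3 AEs in Phase 1 were judged unrelated, although Table 6 lists Grade 3 solicited events. Whether that statement covers them is unclear.

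**Conclusion.** The concern holds as a contradiction between stated rules, and it should be fixed. Read literally, a cluster of Grade 3 solicited reactions would not meet Rule 3 during dosing; read by apparent intent, it would. Rule 1 shares the problem only for non-serious Grade 4 solicited events. The textual conflict is certain. Whether it would cause trouble in operation is less so, because the DSMB Charter could not be checked.

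The figures show only that the readings can differ greatly: 0 against about 53% at a 5% rate, 19% at 2/60 and 1.5% at 1/60. They assume independent participants, equal rates in all four groups and full accrual, so they include fifth events that occur after the last dose, when a pause changes nothing. The rates rest on 1 to 3 participants each and on an earlier formulation. Fever, arthralgia and rash are not covered, because Table 6 lists only the most frequent events. A reader might combine the three event types as if independent and infer a higher overall chance; the overlap in Table 6 does not support that.

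**What to change.** In Protocol 9.2 and SAP 5.2, state that for Rules 1 and 3, Grade 3 or 4 solicited events with onset in the 7-day window count as vaccine-related. Keep the condition of more than 48 hours for fever and pain, and the PI confirmation for fever. Add a cross-reference in 8.2.2 and 8.2.6 so that the waiver of causality assessment does not override the pause rules, and check that the DSMB Charter agrees.

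At the same time, tidy the counting phrase in Rule 3. It most naturally means a count per group with the comparator included, so it should read: at least five participants within any one of Groups A, B, C or D.

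The cost is a few sentences in each document. The downside is that ordinary reactogenicity could pause dosing, with the illustrative chances given in Step 4, and that one non-serious Grade 4 solicited event would do so under Rule 1. The sponsor and DSMB should accept that knowingly. A pause affects only doses not yet given.
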